2.1.2 Exclusion Criteria

- 2.1.2.1 Uncontrolled hypertension ($>150/100$ mmHg).
- 2.1.2.2 Prior external beam radiation therapy to the target lesion(s) within 1 months prior to enrollment
- 2.1.2.3 Prior systemic chemotherapy or therapy with one of the investigational agents within 1 month prior to enrollment.
- 2.1.2.4 Patients who had therapy with one of the investigational agents more than 1 month prior to enrollment in whom tumor genotyping show assignment to the same investigational agent.
- 2.1.2.5 Patients who are receiving any other investigational agents.
- 2.1.2.6 Patients with known brain metastases will be excluded from this clinical trial because of their poor prognosis and because they often develop progressive neurologic dysfunction that would confound the evaluation of neurologic and other adverse events.

- 2.1.2.7 History of allergic reactions attributed to compounds of similar chemical or biologic composition to sunitinib or everolimus.
- 2.1.2.8 Patients who have any severe and/or uncontrolled medical conditions such as:
- unstable angina pectoris, symptomatic congestive heart failure, myocardial infarction ≤ 6 months prior to start of everolimus, serious uncontrolled cardiac arrhythmia, or any other clinically significant cardiac disease
 - symptomatic congestive heart failure of New York heart Association Class III or IV
 - active (acute or chronic) or uncontrolled severe infection, liver disease such as cirrhosis, decompensated liver disease
 - known severely impaired lung function
 - QTc interval > 450 msec for males or > 470 msec for females
 - active, bleeding diathesis;
 - psychiatric illness/social situations that would preclude informed consent, limit compliance with study requirements
- 2.1.2.9 Pregnant or nursing patients will be excluded from the study, because the effects of sunitinib and everolimus on the developing human fetus are unknown. Because there is an unknown but potential risk for adverse events in nursing infants secondary to treatment of the mother with sunitinib or everolimus, breastfeeding should be discontinued if the mother is treated with sunitinib or everolimus (**See also Appendix B**).
- 2.1.2.10 Current treatment with therapeutic doses of Coumadin-derivative anticoagulants (low dose Coumadin up to 2 mg PO daily for deep vein thrombosis prophylaxis is allowed).

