2.3 REGISTRATION PROCEDURES

Authorized staff must register an eligible candidate with NCI Central Registration Office (CRO) within 24 hours of signing consent. A registration Eligibility Checklist from the web site (<http://home.ccr.cancer.gov/intra/eligibility/welcome.htm>) must be completed and sent via encrypted email to: NCI Central Registration Office [contact]. After confirmation of eligibility at Central Registration Office, CRO staff will call pharmacy to advise them of the acceptance of the patient on the protocol prior to the release of any investigational agents. Verification of Registration will be forwarded electronically via e-mail to the research team. A recorder is available during non-working hours.

2.3.1 Treatment Assignment Procedures (For registration purposes only):

Cohorts

Number	Name	Description
1	Cohort 1	Subjects with wild type NETs or mutations in MEN1/PDGFR/KIT/FLT3 or mutations not known to be specifically targeted by sunitinib or everolimus
2	Cohort 2	Subjects with NETs and mutations in NF1/PTEN/PI3K/AKT/mTOR/VH/TP53L but not in MEN1/PDGFR/KIT/FLT3

Arms

Number	Name	Description
1	Arm 1	Sunitinib
2	Arm 2	Everolimus

Arms Assignments

Subjects in Cohorts 1 will be directly assigned to Arm 1.

Subjects in Cohorts 2 will be directly assigned to Arm 2.

Subjects who develop disease progression or unacceptable treatment-related toxicity during treatment in either Arm 1 or Arm 2 will cross-over to the other Arm.

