3.2 STUDY DRUG ADMINISTRATION

3.2.1 Sunitinib Treatment and dose

Patients on Arm 1 will be treated with oral sunitinib at a starting dose of 37.5 mg once daily.

Patients will take sunitinib once daily in the morning, with or without food, as desired. Patients should be advised to drink plenty of water or take rehydration fluids to avoid dehydration if

diarrhea occurs. If a dose is missed the subject will be instructed to take the next dose as scheduled.

- 3.2.1.1 Because hypertension is a known and potentially serious adverse event associated with sunitinib maleate treatment, patients will have their blood pressure monitored and recorded at baseline and weekly during sunitinib treatment either at the doctor's office or using any calibrated electronic device (such as those found at a local drug store or pharmacy). **Appendix E** detail the collection and recording of blood pressure related information.
- 3.2.1.2 Patients with bulky solid tumors should be monitored closely for pneumothorax, intestinal fistulae, or intestinal perforation in the event of rapid tumor destruction.
- 3.2.1.3 Patients should be alerted to the possibility that sunitinib capsules can cause a yellow discoloration of the skin on direct contact. If this happens, the patient should wash immediately with soap and water.
- 3.2.1.4 Thyroid function (free T4, T3 and TSH) will be monitored at every cycle).

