3.2.2 Everolimus Treatment and dose

Patients on Arm 2 will be treated with oral everolimus at a starting dose of 10 mg once daily.

The tablets should be swallowed whole with a glass of water and should not be chewed or crushed. For patients unable to swallow tablets, the tablet(s) should be dispersed completely in a glass of water (containing approximately 30 mL) by gently stirring until the tablet(s) is fully disintegrated (approximately 7 minutes), immediately prior to drinking. The glass should be rinsed with the same volume of water and the rinse completely swallowed to ensure the entire dose is administered.

If vomiting occurs, no attempt should be made to replace the vomited dose. Patients should be instructed that if they miss a dose on one day, they must not take any extra dose the next day, but instead to immediately contact the study center as soon as possible to ask for advice.

Table 3. Choice of targeted therapy driven by the findings of the precise molecular alterations based on common mutations that occur in NETs.

Study Agent	Mutations *	Affected Pathways	
Everolimus	PTEN	PI3K/AKT/mTOR	
	PI3K	PI3K/AKT/mTOR	
	AKT	PI3K/AKT/mTOR	
	mTOR	PI3K/AKT/mTOR	
	VHL	Hypoxia induced PI3K/AKT/mTOR	
	TSC1	PI3K/AKT/mTOR	
	TSC2	PI3K/AKT/mTOR	
	NF1	TSC2/mTOR , Hypoxia induced neoangiogenesis	
Sunitinib	MEN1	Cell growth, cell cycle and genome instability	
	FLT3	Cell survival, proliferation, and differentiation	
	PDGFR	Cell proliferation, cell migration, neoangiogenesis	
	ATM		
	KIT	Cell survival, proliferation, and differentiation	
	ATRX	Cell survival, proliferation, and differentiation	

*Mutations in genes not listed above or that are wildtype will be treated with sunitinib (see [Appendix C](#) for list of other genes that will be genotyped). Germline DNA will be obtained for comparison to tumor genotype data for every patient. Also, some patients with known familial cancer syndromes (*MEN1* and *VHL*) will be included in the study and tumor biopsy for the sole purpose of agent selection in these patients will not be performed.

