11.1.2 Toxicity

(Please see package insert for a complete list of toxicities)

In over 10,000 subjects with solid malignant tumors diarrhea (52.4%), fatigue (49.0%), nausea (42.7%), decreased appetite (38.5%), vomiting (33.9%), palmar-plantar erythrodysesthesia syndrome (28.7%), hypertension (27.6%), stomatitis (26.0%), dysgeusia (25.9%), and mucosal inflammation (25.7%) were the most commonly reported treatment emergent adverse events.

Overall, 60.3% experienced treatment-related AEs of Grade 3, 4, or 5 severity; Grade 3 in 46.9% of subjects, Grade 4 and grade 5 in 11.9% and 1.6% of subjects respectively. The most commonly reported were neutropenia (13.5%), fatigue (9.2%), thrombocytopenia (8.6%), palmar-plantar erythrodysesthesia syndrome (7.4%), diarrhea (6.3%), hypertension (5.5%), and asthenia (5.0%).

Neutropenia (0.3%), fatigue (8.8%), palmar-plantar erythrodysesthesia syndrome (7.4%), thrombocytopenia (6.8%), diarrhea (6.1%); and hypertension (5.4%) were the most commonly reported treatment-related AEs of Grade 3 severity. Neutropenia (3.2%), thrombocytopenia (1.8%), and anemia (0.9%) were the most commonly reported treatment-related AEs of Grade 4 severity. Pulmonary embolism, cardiac failure, death, cerebral hemorrhage, renal failure, myocardial infarction, hepatic failure, gastrointestinal hemorrhage, multi-organ failure, respiratory failure, pneumonia, septic shock, cardiac arrest, sepsis, sudden death, tumor hemorrhage, and hemorrhage, were among the Grade 5 treatment-related AEs reported in at least 3 subjects.

Boxed Warning:

SUTENT has been associated with hepatotoxicity, which may result in liver failure or death. Liver failure has been observed in clinical trials (7/2281 [0.3%]) and post-marketing experience.

Liver failure signs include jaundice, elevated transaminases and/or hyperbilirubinemia in conjunction with encephalopathy, coagulopathy, and/or renal failure. Monitor liver function tests (ALT, AST, bilirubin) before initiation of treatment, during each cycle of treatment, and as clinically indicated. SUTENT should be interrupted for Grade 3 or 4 drug-related hepatic adverse events and discontinued if there is no resolution. Do not restart SUTENT if patients subsequently experience severe changes in liver function tests or have other signs and symptoms of liver failure.

Safety in patients with ALT or AST $>2.5 \times$ ULN or, if due to liver metastases, $>5.0 \times$ ULN has not been established.

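### The 6-month myocardial infarction exclusion (2.1.2.8) is counted from the start of everolimus, so it sets no fixed window before first-line sunitinib, the default arm

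*Combined protocol and SAP*

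**What the plan says.** Exclusion 2.1.2.8 opens with "Patients who have any severe and/or uncontrolled medical conditions such as" and then lists examples. Its cardiac item includes a myocardial infarction at most "6 months prior to start of everolimus, serious uncontrolled cardiac arrhythmia, or any other clinically significant cardiac disease". No other section gives an infarction window, whether counted from enrollment, first study drug or start of sunitinib.

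Section 3.2.1 fixes the first drug for Arm 1: "Patients on Arm 1 will be treated with oral sunitinib at a starting dose of 37.5 mg once daily". Section 2.3.1 defines Cohort 1 as "Subjects with wild type NETs or mutations in MEN1/PDGFR/KIT/FLT3 or mutations not known to be specifically targeted by sunitinib or everolimus", and adds "Subjects in Cohorts 1 will be directly assigned to Arm 1". The footnote to Table 3 (section 3.2.2) agrees: "Mutations in genes not listed above or that are wildtype will be treated with sunitinib". Section 3.1 also sends patients with mutations in both drug groups to sunitinib. Sections 2.3.1 and 3.1.1 move a patient to the other drug only after progression or unacceptable toxicity.

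On sunitinib's cardiac risk, the list in section 11.1.2 that begins "Pulmonary embolism, cardiac failure, death, cerebral hemorrhage, renal failure, myocardial infarction, hepatic failure" ends by stating that these events "were among the Grade 5 treatment-related AEs reported in at least 3 subjects".

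**The concern.** The protocol chose an objective cardiac rule, a fixed number of months after an infarction, but attached it to everolimus alone. For a patient whose first drug is sunitinib, the reference date does not exist when eligibility is checked and may never exist. One site could sensibly apply the window to every candidate, since anyone may later receive everolimus. Another could read it as applying only to patients who start on everolimus. The text does not say which is meant.

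What is at stake is patient safety and consistent eligibility across sites. The protocol's own toxicity section names fatal infarction as a treatment-related event on sunitinib, so nothing in the documents explains why the window should protect only everolimus starters.

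**Working it through.** The plan gives no figure to reproduce. The check sets the sections side by side, with one piece of arithmetic on how far back the window reaches.

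1. **Is the anchor an isolated slip or a pattern?** Exclusions 2.1.2.2, 2.1.2.3, 2.1.2.4 and 2.1.2.18 count from enrollment. Only 2.1.2.8 and 2.1.2.14 (live vaccines) count from everolimus. The anchor fits 2.1.2.14, because section 4.2.3 ties the vaccine caution to everolimus. No comparable drug-specific reason is given for infarction.

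2. **Does the safety text support an everolimus-only window?** Section 11.1.2 lists infarction among fatal sunitinib events. The everolimus summaries in sections 4.1.2 and 11.2.4 do not mention it. Those summaries cover the more common events, so this does not show that everolimus is safer. It shows only that the documents give no basis for limiting the window to that drug.

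3. **How far back does the literal window reach for a sunitinib-first patient?** Let *T* be the months from first sunitinib dose to first everolimus dose, including any gap. The window covers the 6 months before everolimus, so the part falling before the first sunitinib dose is 6 − *T* months, and nothing if *T* is 6 or more.
   - Progression at about 11 months, the historical median PFS used in section 8, with no gap: 6 − 11 = −5. The window opens 5 months after sunitinib began and covers no infarction before it.
   - Progression at the first 3-month scan, with no gap: 6 − 3 = 3. The window reaches back 3 months before sunitinib, not 6.
   - Progression at the first 3-month scan, with the full 3-month gap allowed by section 3.1.1: 6 − (3 + 3) = 0.
   - No cross-over: the window never applies.

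   These cases are illustrations. In all of them the rule can be evaluated only at cross-over, after the patient has already taken sunitinib.

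4. **What about the opposite sequence?** An everolimus-first patient who has an infarction on treatment and then crosses to sunitinib is also outside the literal window, because the infarction follows the start of everolimus.

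5. **Does anything else supply a fixed rule?** Section 2.2 requires a history and an ECG. Section 3.4 repeats the ECG at Cycle 1 Day 1. Sections 2.4 and 3.4 require an echocardiogram in carcinoid patients and a cardiac evaluation in patients with cardiac or pulmonary risk factors; section 2.4 ties the latter to biopsy or surgery. These can detect a recent infarction, but none says how recent is too recent.

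6. **Is the first drug known at the eligibility check?** The sections differ. Section 3.4 places the biopsy under Baseline, after Enrollment, and section 2.3 requires registration within 24 hours of consent. Against that, 2.1.2.4 presupposes a genotype, the specimen table in section 5.1.2 puts the biopsy at Screening, and sections 3.1 and 8 describe genotyping as coming first. The finding does not depend on this, although a drug-neutral anchor works either way.

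**The case against.** The strongest reply is that the same item largely covers the case. The list is illustrative, applies to all candidates, and closes its cardiac line with a catch-all for other clinically important heart disease. Naming infarction as an example already signals that a recent one counts as severe. Unstable angina, symptomatic heart failure, serious arrhythmia and a prolonged QTc exclude whatever the drug. This stands, and it makes the practical gap narrow. It does not close it: the catch-all is a matter of judgement, and it covers *other* cardiac disease after infarction has been given its own limit, so a strict reader could hold that infarction falls under that limit alone.

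A second reply is that every candidate may cross over to everolimus, so the clause is ambiguous rather than wrong. The protective reading is reasonable, but the wording does not state it, and the arithmetic shows that the literal window usually misses the period before sunitinib. The registration checklist mentioned in section 2.3 might settle practice; it is not part of the documents, so its effect is unknown.

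Third, the safety evidence is thin. Section 11.1.2 reports infarction in at least 3 of more than 10,000 subjects, without a rate and without anything on patients with a prior infarction. That stands too. The documents support giving sunitinib an anchor; they do not show that 6 months is the right interval for it.

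**Conclusion.** The concern holds as a wording error. The only fixed infarction window is anchored to the wrong event for the default arm, and no other section repairs it. Confidence is high on the wording. It does not extend to any particular safety consequence.

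The size is low. The patient affected starts on sunitinib, had an infarction in the previous 6 months, and is not judged by the investigator to have clinically significant cardiac disease. Few are likely, which is an assumption: the documents give no rate of recent infarction in this population. Sample size, power, alpha, endpoint and analysis do not change. This could be corrected at the next amendment and does not justify one on its own.

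**What to change.** Reword the infarction part of 2.1.2.8 as: *myocardial infarction within 6 months before the start of study drug (sunitinib or everolimus)*. The eligibility confirmation already required by section 3.1.1 then applies the rule again before the second drug, in either sequence. Leave 2.1.2.14 as it is. Ask the clinical team to confirm that 6 months is the interval they want for sunitinib.

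The cost is a one-line eligibility amendment and an update to the registration checklist. No new procedure is needed, because the history, ECG and cardiac evaluation for patients with risk factors are already in the plan. The downside is that an occasional patient whom an investigator would have accepted will be excluded.

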2.2 SCREENING EVALUATION

Within 4 weeks prior to enrollment

- Confirmation of progressive, histologically or cytologically diagnosed low or intermediate grade, neuroendocrine tumors locally invasive or metastatic confirmed by the Laboratory of Pathology and the Department of Radiology, NCI or a pathology laboratory and radiology department at the enrolling institution (any time prior to enrollment).
- Brain MRI or CT (if clinically indicated)
- 68-Gallium DOTATATE scan per PI discretion
- Contrast enhanced CT scan or MRI of the chest, abdomen and pelvis (CT C/A/P)
- Bone scan for patients in whom bone metastases are suspected
- FDG PET scan
- HIV antibody
- 24-urine collection and measurement of urinary creatinine, total protein and albumin, and serum creatinine measurement

Within 2 weeks prior to enrollment

- Laboratory Evaluations
 - CBC with differential and platelets
 - Chemistries: Sodium (Na), Potassium (K), Chloride (Cl), Total CO₂ (bicarbonate), Creatinine, Glucose, Urea nitrogen (BUN), Albumin, Calcium total, Alkaline Phosphatase, ALT/GPT, AST/GOT, Total Bilirubin, Total Protein
 - INR
 - Lipid panel (fasting)
 - Hemoglobin A1C
- Complete history and physical examination including height, weight, vital signs and ECOG status
- 12 lead ECG

Within 3 days prior to enrollment

- Serum or urine beta-HCG (in women of childbearing potential)

2.3 REGISTRATION PROCEDURES

Authorized staff must register an eligible candidate with NCI Central Registration Office (CRO) within 24 hours of signing consent. A registration Eligibility Checklist from the web site (<http://home.ccr.cancer.gov/intra/eligibility/welcome.htm>) must be completed and sent via encrypted email to: NCI Central Registration Office [contact]. After confirmation of eligibility at Central Registration Office, CRO staff will call pharmacy to advise them of the acceptance of the patient on the protocol prior to the release of any investigational agents. Verification of Registration will be forwarded electronically via e-mail to the research team. A recorder is available during non-working hours.

2.3.1 Treatment Assignment Procedures (For registration purposes only):

Cohorts

Number	Name	Description
1	Cohort 1	Subjects with wild type NETs or mutations in MEN1/PDGFR/KIT/FLT3 or mutations not known to be specifically targeted by sunitinib or everolimus
2	Cohort 2	Subjects with NETs and mutations in NF1/PTEN/PI3K/AKT/mTOR/VH/TP53L but not in MEN1/PDGFR/KIT/FLT3

Arms

Number	Name	Description
1	Arm 1	Sunitinib
2	Arm 2	Everolimus

Arms Assignments

Subjects in Cohorts 1 will be directly assigned to Arm 1.

Subjects in Cohorts 2 will be directly assigned to Arm 2.

Subjects who develop disease progression or unacceptable treatment-related toxicity during treatment in either Arm 1 or Arm 2 will cross-over to the other Arm.

2.4 BASELINE EVALUATION

Studies do not need to be repeated if they have already been performed for screening within the required baseline timeframe.

Within 4 weeks prior to study drug initiation

- Echocardiogram in patients with Carcinoid tumors.
- Patients must provide archival tissue or undergo image guided tumor biopsy for genotyping (patients with known familial cancer syndrome (MEN1, VHL and NF1) are excluded)

- Patients who present with evidence of cardiac or pulmonary risk factors will undergo a cardiac evaluation prior to biopsy/surgical intervention according to standard clinical practice
- 30 mL of peripheral blood for research
- 2-13 mL saliva for research studies
- Hepatitis B and C serology and viral load (if positive serology)

Within 2 weeks prior to study drug initiation

- Laboratory Evaluations
 - Chromogranin A.
 - Only in patients known to have functioning NETs or with a prior history of elevation of secreting biomarkers: vasoactive intestinal polypeptide (VIP), serotonin (urinary 5-HIAA), gastrin, somatostatin, fasting insulin, C-peptide (proinsulin) or glucagon.
- CT C/A/P or MRI

3 STUDY IMPLEMENTATION

3.1 STUDY DESIGN

In this Phase II trial, patients first will undergo tumor genotyping from their archival tumor tissue samples. Patients who do not have archival tumor tissue samples available, will have image guided tumor biopsy. Patients with VHL and MEN1 will not undergo tumor biopsy.

Based on the tumor genotype or germline mutation status, patients will be treated with sunitinib (Arm 1) (for mutations in *MEN1/PDGFR/KIT/FLT3*) or everolimus (Arm 2) (for mutations in *NF1/PTEN/PI3K/AKT/mTOR/VH/TP53L*) daily in 28 day cycles (**Figure 2, Table 3**). Patients will receive long-acting octreotide (for symptoms associated with hormonal hypersecretion). Patients who have gene mutations not known to be specifically targeted by sunitinib or everolimus or with more than one mutation will be assigned to sunitinib (Arm 1) (**Table 3, Appendix C and Appendix D**).

If a patient has two mutations (one in the sunitinib-*MEN1/PDGFR/KIT/FLT3* and another in the everolimus group- *NF1/PTEN/PI3K/AKT/mTOR/VHL/TP53*, the patient will be assigned to sunitinib (Arm 1).

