 - progressive, histologically or cytologically diagnosed low or intermediate grade locally advanced or metastatic NETs.
 - Age \geq 18 years

Design:

- Phase II open labeled clinical trial.
- Tumor biopsy for tumor genotyping will be performed if the patient does not have archival tissue available and does not have MEN1, VHL or NF1.

- Patients with somatic or germline mutations in *MEN1/PDGFR/KIT/FMS*-like tyrosine kinase-3 will be treated with sunitinib (Arm 1).
- Patients with somatic/germline mutations in *NF1/PTEN/PI3K/AKT/mTOR/VHL* will be treated with everolimus (Arm 2).
- Patients with wildtype tumor will be treated with sunitinib (Arm 1).
- Patients who have disease-progression on either sunitinib or everolimus will cross-over to the other drug.
- Treatment will continue until disease progression, unacceptable toxicity, or consent withdrawal.
- Up to 120 patients will be accrued to the study. It is anticipated that 20-30 patients per year may enroll into this trial; thus, accrual may be completed in 4-5 years.

TABLE OF CONTENTS

PRÉCIS 2

TABLE OF CONTENTS..... 4

1 INTRODUCTION 8

 1.1 Study Objectives 8

 1.1.1 Primary Objective: 8

 1.1.2 Secondary Objectives: 8

 1.2 Background and Rationale..... 8

 1.2.1 Neuroendocrine tumors..... 8

 1.2.2 Everolimus 13

 1.2.3 Sunitinib..... 16

 1.2.4 Rationale 20

2 ELIGIBILITY ASSESSMENT AND ENROLLMENT..... 21

 2.1 Eligibility criteria..... 21

2.1.1 Inclusion Criteria 21

2.1.2 Exclusion Criteria 22

 2.2 Screening Evaluation 24

 2.3 Registration Procedures 25

 2.3.1 Treatment Assignment Procedures (**For registration purposes only**):..... 25

 2.4 Baseline Evaluation 25

3 STUDY IMPLEMENTATION 26

 3.1 Study Design..... 26

 3.1.1 Cross-over..... 26

 3.1.2 Long term follow up 27

 3.2 Study Drug Administration..... 28

 3.2.1 Sunitinib Treatment and dose 28

 3.2.2 Everolimus Treatment and dose..... 29

 3.2.3 CCR Self-Administered Study Drugs Policy..... 30

 3.3 Dose Modifications/Dose Delay 30

 3.3.1 Sunitinib..... 30

 3.3.2 Everolimus 35

 3.4 Study Calendar..... 39

 3.5 Criteria for Removal from Protocol Therapy and Off Study Criteria..... 42

 3.5.1 Criteria for removal from protocol therapy 42

 3.5.2 Off-Study Criteria 42

 3.5.3 Off Protocol Therapy and Off Study Procedure 43

4 CONCOMITANT MEDICATIONS/MEASURES 43

 4.1 Supportive Care 43

 4.1.1 Management of Sunitinib-Induced Hypertension..... 43

4.1.2	Management of specific everolimus toxicities	45

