5 BIOSPECIMEN COLLECTION

5.1 SAMPLE COLLECTION FOR GENOTYPING AND RESEARCH STUDIES

5.1.1 Tumor Sample

Within 4 weeks prior to initiation of treatment with the respective study agent (everolimus or sunitinib), patients who meet eligibility criteria, will undergo biopsy of the primary tumor or any metastatic site for molecular analyses. Patients will undergo a percutaneous core needle (16 or 18 gauge) biopsy of the tumor under local anesthesia if there are no paraffin blocks available of tumor sample previously removed or biopsied. These percutaneous biopsies will be performed by interventional radiology (CT scan or ultrasound guidance). If needed, patients will be offered conscious sedation for the biopsy procedure. Sample collection will be performed according to standard operating procedures. Four core needle biopsies will be obtained, three samples will be formalin fixed and sent to the Laboratory of Pathology in the NCI for histological study. The official pathology report and samples will then be taken to [name] laboratory:

[name], Email: [contact]

CANCER GENETICS BRANCH

[name],

[name],

[contact]

The remaining sample will be immediately placed in cryovials, snap frozen on liquid nitrogen or dry ice and transported to [name] laboratory.

Fresh tissue samples should be collected into empty, unused cryovials (Nunc catalog #5001-0012, 5001-1020 or equivalent) on dry ice or liquid nitrogen. Samples may be obtained by FNA or core biopsy.

The interval between sample acquisition and freezing on dry ice must not exceed 30 minutes. Frozen, vialled samples should be transferred from dry ice to -80°C (minimum) or liquid nitrogen frozen storage within 2 hours.

Samples will be recorded in LabMatrix and reviewed by the Laboratory of Pathology to confirm the diagnosis. The remaining sample will be transported to [name] laboratory [[name]., [name], [name], [contact], Email: [contact]] for tumor genotyping along the saliva DNA.

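### Section 3.1 leaves NF1 out of the tumor-biopsy exemption that the précis, Section 2.4 and the study calendar give it, and Section 5.1.1 names no exempt syndrome

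*Combined protocol and SAP*

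**What the plan says.** Section 3.1 (Study Design) sets a general rule, "Patients who do not have archival tumor tissue samples available, will have image guided tumor biopsy", and follows it with one exemption: "Patients with VHL and MEN1 will not undergo tumor biopsy". It then bases treatment on either source of genetic information: "Based on the tumor genotype or germline mutation status".

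Section 5.1.1 (Tumor Sample) says that "patients who meet eligibility criteria, will undergo biopsy of the primary tumor or any metastatic site for molecular analyses". The percutaneous core biopsy is done "if there are no paraffin blocks available of tumor sample previously removed or biopsied". It mentions no familial syndrome.

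Elsewhere the exemption is wider. The précis calls for a biopsy only "if the patient does not have archival tissue available and does not have MEN1, VHL or NF1". Section 2.4 (Baseline Evaluation) adds to its tissue requirement that "patients with known familial cancer syndrome (MEN1, VHL and NF1) are excluded". The study calendar in Section 3.4 names the same three syndromes. Inclusion criterion 2.1.1.4 does not ask patients with any of the three to be willing to have a biopsy. The footnote to Table 3 (Section 3.2.2) mentions only MEN1 and VHL as syndromes for which no biopsy is done to choose the drug.

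**The concern.** Section 3.1 takes up the syndrome exemption expressly and lists two of the three syndromes, with nothing to tell a reader that the list is incomplete. The Table 3 footnote repeats the short list, which makes it look deliberate. A site that follows 3.1, or takes samples from 5.1.1, could biopsy a known NF1 patient whom three other parts of the protocol spare.

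The procedure is invasive. Section 10.4.1.1.2 lists bleeding, infection and visceral injury, and Section 10.4.1.1.3 says that the radiation of the CT-guided biopsy serves research only. The précis assigns germline NF1 to everolimus, so the drug can be chosen without tumor tissue, as for VHL.

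There is also a compliance problem. Section 7.1.8 counts any departure from the approved protocol as a deviation, and Section 7.2.1 requires all deviations to be reported within 7 days. For this patient, either decision departs from some section.

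**Working it through.** The protocol gives no figure to reproduce on this point. The check sets side by side every place that bears on who is biopsied, and applies each to one patient: known NF1, eligible, no archival tissue.

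| Place | Syndromes named | Result for this patient |
|---|---|---|
| Précis, Design | MEN1, VHL, NF1 | No biopsy |
| 2.1.1.4 | MEN1, VHL, NF1 | Willingness to be biopsied not required |
| 2.4 | MEN1, VHL, NF1 | No biopsy |
| 3.4 calendar | MEN1, VHL, NF1 | No biopsy |
| 3.1 | VHL, MEN1 | Biopsy, by the general rule |
| 5.1.1 | None | Biopsy, if there is no paraffin block |
| Table 3 footnote | MEN1, VHL | Silent on NF1; orders no biopsy |

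Three places exempt NF1 directly, one drops the willingness requirement, two lead to a biopsy as written, and one is incomplete without conflicting.

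Two readings need care:

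- The calendar joins the three syndromes to available archival tissue with the word *and*. Taken literally, that could require both. The précis and 2.4 show that a syndrome alone is enough.
- Section 5.1.1 read alone would also send MEN1 and VHL patients to biopsy, which contradicts 3.1 itself. It is best read as an omission, not as a deliberate rule about NF1.

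**Burden per affected patient**

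- Tissue: four cores with a 16- or 18-gauge needle (5.1.1).
- Radiation under CT guidance: 0.80 rem (10.4.1.1.3). Against the 5 rem per year research guideline, 0.80 / 5 = 0.16, or 16%. Against the natural background of 0.3 rem per year cited there, 0.80 / 0.3 = 2.67, or about 2.7 years.
- Radiation under ultrasound guidance, which 5.1.1 also allows: 0 rem. The range is 0 to 0.80 rem.

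**How many patients**

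The documents do not say. Section 1.2.1 puts sporadic tumors at about 85%. If enrollment up to the ceiling of 120 mirrored that (an assumption), familial cases of every kind would number 0.15 × 120 = 18. Known NF1 patients without archival tissue would be only a part of those 18, possibly none.

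**The case against.** The best case on the other side is that this is a drafting slip with a recoverable meaning. The eligibility criteria, the baseline evaluation and the calendar govern day-to-day conduct, and all name NF1. Section 3.1 never says that NF1 patients are to be biopsied; its list is one name short. Section 5.1.1 is about handling samples and was not written to define exemptions. The affected group must have known NF1, a progressive measurable tumor and no stored tissue, although eligibility already requires a histologic or cytologic diagnosis. The radiation figures describe any CT-guided biopsy in the trial and are below the guideline.

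A further point is that tumor tissue is not always uninformative. Section 2.3.1 restricts the everolimus cohort to patients without a MEN1/PDGFR/KIT/FLT3 mutation, and 3.1 sends patients with mutations in both groups to sunitinib. A biopsy could therefore change an NF1 patient's arm.

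Much of this stands. The group is probably small, 5.1.1 is an omission, and the radiation is within the limit and may be zero. But the protocol states no order of precedence among its sections, and 3.1 couples a mandatory rule with an express exemption list. A cytology-only diagnosis may leave no block, so the group cannot be assumed empty. The two-mutation point applies equally to VHL, which 3.1 does exempt, so it gives no reason to treat NF1 differently.

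**Conclusion.** The concern holds. Section 3.1, and 5.1.1 by omission, disagree with the précis, 2.4 and the calendar on whether a known NF1 patient without archival tissue has a biopsy. The three-syndrome rule is evidently the intended one, since it appears in the design summary, the baseline procedures and the calendar and agrees with inclusion criterion 2.1.1.4. If the sponsor did mean NF1 patients to be biopsied, those four places would need changing instead; either way one rule is needed.

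Confidence in the text comparison is high. The consequence is an avoidable invasive research procedure for an unknown and probably small number of patients. The sample size and power are unaffected, and no effect on PFS is shown. The wording should be corrected because the risk falls on patients the protocol meant to spare.

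**What to change.** Use one list, MEN1, VHL and NF1, in all three places:

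- **Section 3.1:** reword the exemption as *Patients with known MEN1, VHL or NF1 will not have a tumor biopsy.*
- **Table 3 footnote:** add NF1 beside MEN1 and VHL.
- **Section 5.1.1:** open with *Except for patients exempt under Section 2.4 (known MEN1, VHL or NF1)*.

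The assignment rules can stay as they are. The cost is a wording amendment to these three places, with no added procedure, patient or data item.
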